# 3.3.9.2. GAIN TM medium

Single-step culture medium for the in vitro culture of human embryos and gametes GAIN™ medium is sterilized by sterile filtration. Medium is a ready to use. Medium is a bicarbonate-buffered balanced salt solution with 10 mg/liter gentamicin and 3.5 g/liter human serum albumin. GAIN™ medium should generally be used in an incubator at 37°C set at 5% CO at normal atmospheric pressure

COMPOSITION GAIN™ medium is a bicarbonate-buffered balanced salt solution with 10 mg/liter gentamicin and 3.5 g/liter human serum albumin.

Ministry of Higher Education and Scientific Research Al-Nahrain University High Institute for Infertility Diagnosis and Assisted Reproductive Technologies

Study the Effects of Intrauterine flushing with Low Dose Human Chorionic Gonadotrophin on Endometrial Receptivity and ICSI Outcome

OCTOBER 16, 2024

CHAPTER FOUR RESULTS

Statistical analysis

The data analyzed using Statistical Package for Social Sciences (SPSS) version 26. The data presented as mean, standard deviation and ranges. Categorical data presented by frequencies and percentages. Independent t-test and Analysis of Variance (ANOVA) (two tailed) was used to compare the continuous variables accordingly. Paired t-test was used to compare the continuous variables on pickup day and on transfer day. Chi square test was used to assess the association between categorical variables, while fisher exact test was used instead when the expected frequency was less than 5. A level of P – value less than 0.05 was considered significant.

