# **Chapter Three Patients, Materials and Methods**

A prospective comparative study was conducted in the High Institute for Infertility Diagnosis and Assisted Reproductive Technologies, Al-Nahrain University in Baghdad, from January 2023 to January 2024. Ninety Iraqi women were included in this study. Every patient gave her written informed consent before taking part in the study figure (3-1), which was approved by the Ethical Committee of High Institute for Infertility Diagnosis and Assisted reproductive Technologies, Al-Nahrain University. They were evaluated twice during the study period and they did not receive any monetary compensation for their participation.

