## 3.3. Methods

# 3.3.1. Patients' assessment and study design

A comprehensive medical, surgical, and obstetrical history was gathered from couples experiencing infertility, as per a structured questionnaire illustrated in figure (3-2). Thorough examinations were conducted on infertile women, encompassing both general and gynecological assessments. Height and weight measurements were taken to calculate the body mass index (BMI) using the formula BMI = weight (kg) / [height (m)]2. Initial hormonal evaluations were performed on either the second or third day of the menstrual cycle for all female subjects. Procedures such as transvaginal ultrasound, saline infusion sonography (SIS), and hysterosalpingography (HSG) were carried out to evaluate the uterine cavity, confirm tubal patency, and in some cases, laparoscopy was employed to assess tubal patency and exclude pelvic abnormalities. Seminal fluid analysis was conducted for the male partners. All infertile women enrolled underwent the application of the Gonadotropin Releasing Hormone (GnRH) antagonist ovarian hyperstimulation protocol, known as the flexible protocol. The follow-up of

patients included serial vaginal ultrasound and monitoring of serum estradiol levels. Subsequently, ovum pick up (OPU) was carried out post ovulation triggering approximately 35-36 hours later. Doppler ultrasound, along with measuring serum TNF and IL-10 levels, was performed for all participants on the day of OPU, followed by additional measurements on the day of embryo transfer. Evaluation of oocytes' morphology and recording of maturation rate (MR) were conducted, leading to Intracytoplasmic Sperm Injection (ICSI) of apparently normal Metaphase II (MII) oocytes. The morphological assessment of embryos was done, and the count of different embryo grades was noted. Luteal phase support, embryo transfer, and serum beta-human chorionic gonadotropin (B-hCG) evaluation were done on day 14 post embryo transfer, with the recording of biochemical pregnancy rate (Figure 3.3).

0.	Case no.		LMP		Protocol flexible antagonist day of cetrotide     type of trigger cd dose					
	age	HT.	WT.	BMI	Urasound	Base line US	5	Day of pick up	dıy Embrya	tranfer
and	Age	Occupant.	telephone		E.T. hype echoic (triple)					
					Hyper ochoic (non-triple)					
of infert.	duration				Sub endometrial flow RI					
					п					
of infer.	Tubal	Ovulatory	Male factor	Un e	VMAX					
eminal fluid analysis:		he			V MIN					
					1210	-				

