#### **3.3.4.7.** Luteal Phase Support

The luteal phase was maintained starting from oocyte retrieval day through the administration of vaginal progesterone (Cyclogest®400mg twice daily; Actavis, UK®) and progesterone injection (depote 250-500 mg twice weekly) for a duration of 14 days. This regimen continued until the  $\beta$ -HCG test was conducted; in case of a positive result, progesterone intake was sustained until 9-12 weeks, coinciding with the initiation of placental activity (Zhang et al. 2020).

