#### **3.3.5. Samples collection**

### 3.3.5.1. Blood Sampling

Blood Sampling for TNF- $\alpha$  & IL-10, on the day of OPU and day of embryo transfer for both hCG group together with control group and according to the number and grading of the embryos, patients were prepared for the transfer. The patient's serum was obtained by aspirating the blood samples from the median cubital vein by disposable syringe (Becton Dickinson company, USA), into a serum separating tube (gel & clot activator, AFCO, Jordan), and allowed to clot for 30 minutes. Serum was obtained after centrifugation at a rate of 5000 rpm for 5 minutes. All samples were kept in a sterile container labeled with patient's study number. Samples were refrigerated at -20°C until the time of examination using diagnostic Kit by (ELIZA) technique (IL-10, TNF, ELIZA Kit, Bio Source, USA).

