## **3.3.9. HCG-Intrauterine Infusion**

HCG-intrauterine infusion done for 60 women undergoing ICSI to improve endometrial receptivity. Two different doses of hcg (diclair R)1500 IU were used for each patient. Drug was used on day of ova pick up. In the study group, the patient was put in the lithotomy position, and the cervix was visualized using Cusco's speculum. The cervical mucous was wiped out using a sterile piece of gauze, then the mucous was partially removed by gentle suction with a 1-mL syringe. A dummy ET was performed using a soft catheter (Wallace-Smiths Medical International Ltd.); if the soft catheter did not easily pass the internal cervical os, another more rigid but malleable catheter (Cook IVF) was used. After the catheter had passed the internal cervical os.

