# 3.3.9.1. Preparation of hCG

HCG dose was prepared by using , 1 ml of tissue culture media (G.2 plus ref. 10132, Vitrolife) to one vial containing 1500 IU of hCG (Diclair®). The injection dissolved immediately after completion of ova pick up and infused directly to endometrial cavity. 35  $\mu$ L of tissue culture mediam containing 500, or 47  $\mu$ L of tissue culture media containing 700 IU of hCG was injected intrauterine. Dose prepared by using (1 ml) of gain medium to dissolve hcg injection and dose for each patient loaded by using IUI (Gyntics) catheter.

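### The only stated analysis using both pick-up-day and transfer-day values is a paired t-test, which cannot isolate an hCG effect; no between-group test is stated to use the pick-up value

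*SAP*

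**What the plan says.** The SAP's Statistical analysis paragraph is the whole analysis plan; the protocol adds no analysis text. Two sentences matter here. For comparisons of continuous variables: "Independent t-test and Analysis of Variance (ANOVA) (two tailed) was used to compare the continuous variables accordingly". For the two measurement days: "Paired t-test was used to compare the continuous variables on pickup day and on transfer day". Neither names a change score, a covariate, a repeated-measures model or a group-by-time term, and the second does not say whether the paired test was run within each group or over all women.

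The protocol describes the data. Section 3.3.1 has Doppler together with "measuring serum TNF and IL-10 levels, was performed for all participants on the day of OPU", then further measurements on the day of embryo transfer. Section 3.3.5.1 confirms that blood was taken "on the day of OPU and day of embryo transfer for both hCG group together with control group". Section 3.3.9.1 places the infusion right after retrieval: "The injection dissolved immediately after completion of ova pick up and infused directly to endometrial cavity". It does not say whether that day's blood sample and Doppler came before or after it. Section 3.3.4.7 says of progesterone support: "The luteal phase was maintained starting from oocyte retrieval day". The design is given as "A prospective comparative study was conducted", and no random allocation is described.

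**The concern.** The study asks whether intrauterine hCG changes endometrial receptivity. A paired t-test asks whether a variable differs between two days. These are different questions, because every woman, control or treated, had been triggered, had undergone retrieval and started progesterone on retrieval day. Values may therefore move between the two days in all groups without any hCG effect.

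Neither way of running the paired test solves this. Run by group, it invites the reading that hCG works if an hCG group is significant and the controls are not; that contrast of p-values is not a test of the difference between groups. Run over all women, it mixes treated and untreated.

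The between-group t-test or ANOVA is the proper place for the treatment question. As stated, it makes no use of the pick-up value. That gives up precision and, with no randomisation described, leaves any measured pick-up-day difference between groups unaccounted for.

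**Working it through.** The plan gives no sample-size, power, effect-size or correlation figure, so there is nothing of its own to reproduce. The figures below illustrate size under stated assumptions.

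**Inputs from the documents.** 90 women (protocol, Chapter Three opening); 60 infused (section 3.3.9: "HCG-intrauterine infusion done for 60 women undergoing ICSI to improve endometrial receptivity"), so 90 − 60 = 30 controls; significance level 0.05 (SAP).

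**Assumptions.** A 30/30 split of the 60 infused women; equal SD on both days; correlation r between days of 0.3 to 0.7; a change common to all groups of 0 to 1 SD; a true group difference of 0.5 SD for power.

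**1. Paired tests by group, no hCG effect.** In SD units the SD of change is √(2(1 − r)), which is 1.00 at r = 0.5 and 0.775 at r = 0.7. The probability p that one group of 30 is significant comes from the noncentral t with noncentrality (change / SD of change) × √30. At least one hCG group significant and controls not has probability (1 − (1 − p)²)(1 − p), with a maximum of 0.385 at p = 0.42.

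| Common change (SD) | 0 | 0.1 | 0.2 | 0.3 | 0.5 | 0.7 | 1.0 |
|---|---|---|---|---|---|---|---|
| r = 0.5 | 0.093 | 0.145 | 0.274 | 0.377 | 0.231 | 0.040 | 0.000 |
| r = 0.7 | 0.093 | 0.178 | 0.345 | 0.364 | 0.072 | 0.002 | 0.000 |

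The pattern is worst for modest changes. It vanishes for large ones, because controls then become significant too.

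**2. Paired test pooled over 90 women, r = 0.5.** Noncentrality is change × √90. The test is significant with probability 0.804 at 0.3 SD and 0.997 at 0.5 SD, again with no hCG effect.

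**3. Precision of the between-group test.** Relative to the transfer-day value alone, the error variance is 1 − r² with ANCOVA: 0.91, 0.75 and 0.51 at r = 0.3, 0.5 and 0.7, that is, cuts of 9%, 25% and 49%. For a change score the factor is 2(1 − r): 1.4, 1.0 and 0.6. Two-group power for 0.5 SD with 30 per group:

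| r | Unadjusted | ANCOVA | Change score |
|---|---|---|---|
| 0.3 | 0.48 | 0.51 | 0.37 |
| 0.5 | 0.476 | 0.583 | 0.478 |
| 0.7 | 0.478 | 0.755 | 0.694 |

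For the three-group test with both hCG groups shifted by 0.5 SD, power is 0.49 unadjusted, 0.61 with ANCOVA at r = 0.5 and 0.78 at r = 0.7.

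**4. False positives when groups differ by 0.3 SD at pick-up (simulation, 40,000 runs, two groups of 30, no hCG effect).**

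| Pick-up difference | r | Unadjusted | ANCOVA | Change score |
|---|---|---|---|---|
| Shrinks to 0.3r by transfer | 0.5 | 0.091 | 0.051 | 0.088 |
| Shrinks to 0.3r by transfer | 0.7 | 0.125 | 0.048 | 0.071 |
| Persists in full | 0.5 | 0.208 | 0.097 | 0.049 |
| Persists in full | 0.7 | 0.210 | 0.077 | 0.049 |

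At r = 0.3 the ANCOVA rate is about 13% if the difference persists, against 21% unadjusted.

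These rates are for a systematic difference. A chance observed pick-up difference of 0.25 to 0.35 SD leaves the unadjusted rate at 0.059 (r = 0.5) or 0.054 (r = 0.7).

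**The case against.** The SAP never calls the paired t-test its test of hCG. It names between-group tests in the same paragraph, and the word accordingly does not rule out change scores. An unadjusted comparison of transfer-day values is a valid test if the groups are comparable; its error rate stays near 5% after a chance imbalance, and the documents give no evidence of a systematic one. The gain from adjustment depends on an unknown correlation: at r = 0.3 it is 0.51 against 0.48. Without randomisation ANCOVA is not uniformly best either, since a persisting pick-up difference leaves it with 8% to 13% false positives, while the change score holds 5%. If the pick-up sample followed the infusion, the covariate is unsafe and the fallback is a comparison the SAP already allows.

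Much of this stands as a limit on reach. A between-group test does exist, the misreadings of paired p-values are possible rather than documented, and the magnitudes are illustrative. It does not defeat the point. The paragraph still states no between-group analysis that uses the pick-up value, and ANCOVA did better than the unadjusted test in every power and systematic-imbalance scenario examined, r = 0.3 and a persisting imbalance included. The uncertainty between ANCOVA and change score is a reason to report both. The unstated order of sampling and infusion must be settled before either is interpreted.

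**Conclusion.** The concern holds. The one stated joint use of the two days cannot attribute change to hCG, and no stated between-group test uses each woman's pick-up value although it was collected in all groups. With no hCG effect, the by-group pattern that looks like a treatment effect arises in about 0% to 38% of studies, and a pooled paired test is significant in 80% to over 99% at changes of 0.3 to 0.5 SD (r = 0.5). The cost to the between-group test is lost power (0.48 against 0.51 to 0.76 over r = 0.3 to 0.7) and exposure to any systematic pick-up-day imbalance.

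Confidence is high on the omission. The sizes rest on assumed correlations, changes, imbalances and an equal split of the infused women. The point covers only outcomes measured on both days, not pregnancy. It should be corrected, but it does not invalidate the stated between-group test.

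**What to change.** For each outcome measured on both days (TNF, IL-10, the Doppler indices, and endometrial thickness if recorded on both):

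- Make the treatment test an ANCOVA of the transfer-day value on group and pick-up-day value. Report the two-degree-of-freedom group test, then Tukey-adjusted A−C, B−C and A−B differences with 95% confidence intervals.
- State whether pick-up-day blood and Doppler were obtained before the infusion. Use the pick-up value as covariate only if they were; otherwise report the unadjusted transfer-day comparison and say why.
- Add a between-group comparison of change scores as a sensitivity analysis, subject to the same check on timing. State that adjustment removes measured pick-up-day imbalance only and does not replace randomisation.
- Keep the paired t-tests as description, labelled by group or pooled. If the ANOVA was in fact run on change scores, say so.

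The cost is one standard SPSS procedure on existing data, one degree of freedom, and a check of records for the order of sampling and infusion. Any significant within-group change would no longer count as evidence of an hCG effect.

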# 3.1.1. Patient classification

- Group A: patients who receive (700IU) of intrauterine hCG
- Group B: patients who receive (500IU) of intrauterine hCG
- Group C: Control group patients did not receive any treatment.

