# 3.1.2. Inclusion criteria

• All couples undergoing IVF / ICSI protocols reaching the day of embryo transfer with grade 1 (G1) embryos.

• Age of women was (18-40) years old.

• Infertility due to female factors: tubal blockage, un ovulatory cycles, unexplained infertility.

- Infertility due to male factors.
- fresh cycle transfer

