# **3.1.3.** Exclusion criteria

• All cases of endometrioses whether suspected clinically or diagnosed laparoscopically.

- Cases of congenital anomalies of the reproductive system.
- Patients aged more than 40 year
- Those not having G1 embryos.

• Cases with chronic systemic diseases (diabetes, blood disease, hypertension, connective tissue and autoimmune diseases, asthma, class II and III obesity, thyroid disturbance).

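### Every between-group test in the SAP is unadjusted and the supplied text shows no random allocation, so a prognostic difference between groups, if present, would shift the hCG estimate uncorrected

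*SAP*

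**What the plan says.** **Design.** The opening of Protocol Chapter Three reads "A prospective comparative study was conducted in the High Institute for Infertility Diagnosis", and gives the period and size as "from January 2023 to January 2024. Ninety Iraqi women were included in this study". Section 3.1 says the women were selected from those attending the institute. Section 3.1.1 defines the groups by what they received: 700 IU of intrauterine hCG, 500 IU, or nothing ("Control group patients did not receive any treatment"). Section 3.3.9 puts 60 women in the infused groups combined, without a split by dose. The supplied text does not say how a woman came to be in a group.

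**Population.** Section 3.1.2 states "Age of women was (18-40) years old" and admits tubal, anovulatory, unexplained and male-factor infertility. Section 3.1.3 removes several conditions and also excludes "Those not having G1 embryos". All women had a flexible antagonist protocol (3.3.4.1.a) and fresh transfer (3.1.2).

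**Outcomes.** Pregnancy is tested on day 14 after transfer (3.3.1, 3.3.8). For the markers, 3.3.1 says "Doppler ultrasound, along with measuring serum TNF and IL-10 levels, was performed for all participants on the day of OPU", with further measurements on the day of transfer.

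**Analysis.** For continuous variables the SAP states "Independent t-test and Analysis of Variance (ANOVA) (two tailed) was used to compare the continuous variables accordingly". For categorical variables it states "Chi square test was used to assess the association between categorical variables", with Fisher's exact test when the expected frequency is below 5. A paired t-test compares pick-up day with transfer day. The SAP names no regression, ANCOVA, stratification or covariate.

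**The concern.** A crude comparison estimates the effect of hCG only if the groups are alike in everything else that drives the outcome, apart from chance. Random allocation secures that; the supplied text does not show it. Age and cause of infertility vary among eligible women and may bear on pregnancy. The restriction to grade 1 embryos, the exclusions and the common stimulation protocol narrow that spread but do not balance it across groups.

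If one group were, for example, younger, part of any difference in pregnancy, Doppler indices, TNF-alpha or IL-10 would come from age and be reported as an effect of hCG. The paired t-test does not help, because it compares days within women and not groups. At stake is how the reported differences are interpreted: without an adjusted estimate, a reader cannot see whether a result survives allowance for even the most obvious prognostic factor.

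**Working it through.** The plan gives no expected rate, SD, effect size or power, so it has no figure to reproduce. The check asks how far the SAP's own tests would be misled by a prognostic difference when hCG does nothing.

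**From the documents.** 90 women in total, 60 infused, so 90 - 60 = 30 controls. Two-sided level 0.05. Pearson chi-square, or Fisher's exact test if an expected count is below 5.

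**Assumed.** The infused women split 30/30 by dose. Pregnancy is 40% in better-prognosis women and 30%, 25% or 20% in the rest. The share of better-prognosis women is 60% v 40%, or 70% v 30%.

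**Pregnancy, one pair of groups, 30 v 30.** With share s of better-prognosis women, the group rate is s × 0.40 + (1 - s) × q, where q is the rate in the rest. For s = 0.6 v 0.4 and q = 0.30: 0.24 + 0.12 = 0.36 against 0.16 + 0.18 = 0.34. The odds ratio is (0.36/0.64)/(0.34/0.66) = 1.09. The false-positive rate sums the exact binomial probabilities of all tables with p < 0.05.

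| Shares | q | Rates | Spurious OR | False positives |
|---|---|---|---|---|
| 60/40 v 40/60 | 0.30 | 0.36 v 0.34 | 1.09 | 5.1% |
| 60/40 v 40/60 | 0.25 | 0.34 v 0.31 | 1.15 | 5.5% |
| 60/40 v 40/60 | 0.20 | 0.32 v 0.28 | 1.21 | 6.1% |
| 70/30 v 30/70 | 0.30 | 0.37 v 0.33 | 1.19 | 5.9% |
| 70/30 v 30/70 | 0.25 | 0.355 v 0.295 | 1.32 | 7.5% |
| 70/30 v 30/70 | 0.20 | 0.34 v 0.26 | 1.47 | 10.1% |

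With no imbalance the test rejects 4.8-4.9% of the time.

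**Scale.** The spurious differences are 2-4 and 4-8 percentage points. The standard error of a difference, √(2p(1 - p)/30), is 0.112 at p = 0.25 and 0.126 at p = 0.40. The shifts are therefore below one standard error: the main effect is a displaced estimate, not a high false-positive rate.

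**Could chance alone do this?** For a factor present in half the women and two groups of 30 formed at random, a gap of at least 20 points has probability 0.155 and a gap of at least 40 points 0.0027. The 60/40 case is compatible with randomisation; the 70/30 case would hardly arise without selection.

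**Continuous outcomes, 30 v 30.** The spurious shift in SD units is d × r, where d is the age difference in SDs and r the correlation of age with outcome. Assuming d = 0.25-0.5 and r = 0.2-0.4, it runs from 0.25 × 0.2 = 0.05 to 0.5 × 0.4 = 0.20 SD. The standard error is √(2/30) = 0.258 SD, and the t-test (58 df) rejects 5.4-11.9% of the time.

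**Sensitivity to the assumptions.** With pregnancy rates of 45% v 20% and an 80/20 v 20/80 split, the 30 v 30 false-positive rate is 23.0%; with 50% v 15% it is 40.8%. The size follows the chosen inputs.

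**Limit.** These are two-group calculations. The SAP does not say whether chi-square is applied to all three groups or to pairs, and no three-group test was modelled.

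**The case against.** The strongest reply is that nothing here shows a defect. Part of the front matter was removed and Figure 3-3, the study-design figure, is not shown, so an allocation step may exist out of sight. Under random allocation the chi-square and t-tests are valid as they stand. The illustrated shifts are small, rest wholly on assumed inputs and model pairs only. The listed tests could also be run on age and cause of infertility as a baseline comparison. Finally, about 90 women support little modelling, and recruitment has ended.

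Much of this stands. A reader might infer that the study was not randomised, or that the groups were imbalanced and the results are confounded. The documents support neither: they are silent on assignment where we can read them and give no group characteristics. Nor do they support a claim that false positives are badly inflated.

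What survives is narrower. Adjustment for age is worthwhile under either kind of allocation: if assignment was not random it removes measured confounding by age, and if it was random it allows for chance imbalance and can sharpen the continuous comparisons. A baseline table could show an imbalance but would not correct the estimate. Small numbers limit the model to a few parameters; they do not rule it out.

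**Conclusion.** The point holds as a recommended change to the analysis. All named between-group tests are unadjusted, eligible women differ in age and cause of infertility, and no random allocation is shown in the supplied text. If the groups differ in prognosis, the hCG estimate is shifted, and no listed analysis would show by how much. The existence, size and direction of any imbalance are unknown. Under the moderate assumptions used, the spurious odds ratio is 1.09-1.21 for a 60/40 split and 1.19-1.47 for a 70/30 split. These figures are illustrations of the mechanism, not estimates for this trial.

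**What to change.** Keep the crude tests and, however women were allocated, add two analyses.

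1. **Pregnancy.** Logistic regression on three-level group and woman's age, with Firth's penalty if events are few, and at most one further factor fixed before the infusion and costing one parameter (for example, duration of infertility). Report an overall group test and odds ratios with 95% confidence intervals for each hCG group against control.
2. **Transfer-day Doppler, TNF-alpha and IL-10.** ANCOVA on group and age, plus the pick-up-day value where it was taken before the infusion. Protocol 3.3.1, 3.3.5.1 and 3.3.9.1 put measurement and infusion on the same day without giving their order, so this must be confirmed first.

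Label both analyses post hoc if the data have already been examined; recruitment ran to January 2024, and the SAP text is in the past tense under a results chapter dated October 2024. Word conclusions as association unless allocation was random. A sentence stating how women were assigned and how many were in each group would help the reader, but the adjusted analyses should not wait on it.

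**Cost.** A few models on variables already on the questionnaire (Figure 3-2), with no new data. If 25-40% of women conceive (assumed), there are 90 × 0.25 = 22.5 to 90 × 0.40 = 36 events. Group and age use three parameters, leaving 7.5-12 events each; a fourth leaves 5.6-9. Odds-ratio intervals will be wide, and selection on unmeasured factors remains.

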## **3.3.8.** Pregnancy Test (P.T)

Pregnancy is documented by an elevated serum  $\beta$ -hCG level of  $\geq 6.5$  mIU/l in the 14th day following embryo transfer, and Progesterone treatment was continued up to 12 gestational weeks (Vaisbuch et al., 2012). Ultrasound examination is performed 6th week after E.T in order to confirm clinical pregnancy, viability and for diagnosis of multiplicity.

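### One P<0.05 rule for three groups and several outcomes, with no primary outcome and no multiplicity adjustment, puts the false-positive risk well above 5%

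*SAP*

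**What the plan says.** The SAP's statistical analysis paragraph is the whole plan. Its decision rule is one sentence, under which a P-value "less than 0.05 was considered significant". For continuous measures, "Independent t-test and Analysis of Variance (ANOVA) (two tailed) was used to compare the continuous variables accordingly". For categorical ones, "Chi square test was used to assess the association between categorical variables", with Fisher's exact test for small expected counts. A paired t-test compares pick-up day with transfer day. The paragraph does not say which groups are compared by which test, whether a significant ANOVA must come before any t-test, or whether any P-value is adjusted.

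Protocol section 3.1.1 defines three groups: two hCG doses (the first is "Group A: patients who receive (700IU) of intrauterine hCG") and an untreated control. The outcomes are spread through the methods:

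- TNF-alpha and IL-10 (3.3.1, 3.3.5.1)
- endometrial thickness (3.3.7.1)
- RI and PI (3.3.7.2)
- biochemical pregnancy on day 14 (3.3.1)
- a later scan "in order to confirm clinical pregnancy, viability and for diagnosis of multiplicity" (3.3.8)

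Section 3.3.1 also notes that "recording of maturation rate (MR) were conducted", and fertilisation and embryo grade are recorded in 3.3.4.5. No supplied section names a primary outcome or gives a sample-size basis.

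**The concern.** A 5% threshold limits the error of one test. Applied separately to several outcomes and possibly several group pairs, it does not limit the chance that something comes out significant when hCG does nothing. With no main outcome named, any isolated P<0.05 could be presented as showing that intrauterine hCG improves receptivity or ICSI outcome, which is the question in the study title. This is more than a missing detail, because following the rule exactly as written produces the inflated error rate.

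**Working it through.** **Stated figure.** The plan gives no family-wise error rate, power or sample-size calculation to reproduce. The per-test level of 0.05 is the only error figure.

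**Inputs from the documents.** Total 90 women (Protocol, opening of Chapter Three), of whom 60 were infused (3.3.9), so 90 − 60 = 30 controls. Tests are two-sided at 0.05 (SAP). Post-infusion outcomes counted: thickness, RI, PI, TNF-alpha, IL-10, biochemical pregnancy and clinical pregnancy, seven in all. Pick-up-day values are treated as baseline, because section 3.3.9.1 places the infusion after pick-up.

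**Assumed inputs.** 30 women at each dose; 40% biochemical pregnancy, 85% of those clinical; a common correlation of 0 to 0.5 among the remaining outcomes.

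**Step 1: one continuous outcome.** Three independent tests would give 1 − 0.95³ = 14.3%. The three pairs share groups, so the true figure is lower: simulation with 30 per group gives 11.95%, or about 12%.

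**Step 2: overlap between outcomes.** From section 3.3.7.2, RI = (PSV − EDV)/PSV, so EDV = PSV(1 − RI). The mean velocity is then (PSV + EDV)/2 = PSV(2 − RI)/2, and

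PI = (PSV − EDV)/mv = PSV·RI ÷ [PSV(2 − RI)/2] = 2RI/(2 − RI).

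Under the Protocol's own formulas PI is a one-to-one function of RI, so the two tests are effectively one. Clinical pregnancy is treated as a subset of biochemical pregnancy. Seven outcomes therefore behave like five to six.

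**Step 3: hand check at zero correlation.**

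- One global test per outcome: 1 − 0.95⁵ = 22.6%; 1 − 0.95⁶ = 26.5%.
- All three pairs: 1 − (1 − 0.1195)⁵ = 47.1%; 1 − (1 − 0.1195)⁶ = 53.4%.

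**Step 4: simulation with both links built in.** The table gives the chance of at least one false P<0.05 between groups, from 4,000 runs per setting:

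| Comparisons run | corr. 0 | 0.3 | 0.5 | Range over repeat runs |
|---|---|---|---|---|
| One global test per outcome | 25% | 24% | 22% | 21–25% |
| Both hCG-v-control pairs, unadjusted | 40% | 38% | 35% | 34–41% |
| All three pairs, unadjusted | 50% | 48% | 44% | 43–52% |

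The global and all-pairs rows agree with the hand check.

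**Step 5: sensitivity to the outcome count.** These runs ignore the links in step 2, use a 35% pregnancy rate and take correlation from 0.7 to 0:

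| Outcomes | Global only | hCG-v-control pairs | All pairs |
|---|---|---|---|
| 4 | 14–19% | 24–31% | 31–41% |
| 7 | 21–31% | 33–49% | 41–60% |
| 9 | 24–37% | 38–56% | 46–68% |

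The most favourable cell, 14%, is still nearly three times the nominal 5%. Paired t-tests are left out of all these figures. Values may change between pick-up and transfer without any hCG effect, so a significant within-group change is not evidence of one, and reading it as such would add to the error.

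**The case against.** The strongest objection is that the SAP never says every pair of groups is tested. A reader might infer this from the independent t-test, which compares only two groups, being listed beside ANOVA. But it could equally serve pooled hCG against control, or pregnant against not pregnant. This objection stands: all-pairs testing is one reading, and only the global-test figure avoids assuming it. The SAP does not exclude the other readings either, and it adjusts none of them.

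A second objection also stands. A significant difference between groups A and B is a dose contrast, not an effect of hCG against none. Some false positives would also point against hCG. Counting only results in its favour, 14 hCG-versus-control tests at 0.025 each give at most 1 − 0.975¹⁴ = about 30%.

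Third, treating the tests as independent overstates the risk. It gives 1 − 0.95²¹ = 65.9% for 21 tests, or 1 − (1 − 0.1195)⁷ = 59% for seven separate outcomes. RI and PI, and the two pregnancy outcomes, are not separate. Counts of expected false positives that add an omnibus test and three pairs for every outcome likewise presume an analysis the SAP does not state.

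None of this brings the risk near 5%.

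**Conclusion.** The defect holds on every reading examined: no primary outcome in the supplied text, no multiplicity control and one 0.05 threshold for all tests. Its size is a range, because the SAP leaves the comparisons open: about 21–25%, 34–41% or 43–52% for the three sets of comparisons in step 4. These figures rest on the assumed equal dose groups, pregnancy rates and correlations, and on the outcome list taken from the Protocol.

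A reader might infer that a false hCG effect is about as likely as not. The documents do not support that as a general statement. It needs all three pairs to be tested unadjusted, and it counts the dose contrast as an hCG effect.

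A reader might also think that naming a primary outcome now would restore a 5% error rate. It would not. The study ran to January 2024 and the SAP is dated October 2024, so any choice made in it comes after the study period.

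**What to change.** Replace the SAP's significance sentence with rules to this effect:

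1. **Continuous outcomes.** Use the three-group ANOVA, then A v C, B v C and A v B contrasts adjusted by Tukey or Holm, in place of unadjusted independent t-tests between groups.
2. **Pregnancy outcomes.** Use the three-group chi-square or Fisher test, then Holm-adjusted pairs, each with a risk difference and 95% CI.
3. **Across outcomes.** Apply Holm across the outcomes before calling any hCG effect significant. With seven global P-values the first step is 0.05/7 = 0.0071. This controls the error if hCG affects nothing. A guarantee for every individual pair needs Holm over all 21 pairwise P-values, with first step 0.05/21 = 0.00238.
4. **Status of the results.** State that no outcome was named as primary before the data were collected. If clinical pregnancy is presented as the main outcome, disclose that it was chosen afterwards. Label all P-values exploratory, including that one.
5. **Laboratory measures.** Report maturation, fertilisation and embryo grade as comparability measures. Maturation describes oocytes already retrieved at infusion, and the other two are assessed in culture, outside the uterus.

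If the sections omitted from the supplied text do name a primary outcome, item 4 should cite that instead.

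The cost is SAP wording and a re-run on existing data, with no new measurements. The downside is fewer nominally significant results: within one outcome, the first Holm step for three pairs is 0.05/3 = 0.0167.
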